8.6 Sample Size Justification for Secondary Endpoints

In Figure 5, a set of power curves is presented to describe the power to detect treatment effects for secondary endpoints. These power calculations are based on the following assumptions: 2-sided Type I error rate of 0.05, a test statistic based on a 2-sample t-test, and sample sizes ranging from 350 to 550 subjects per treatment group. Mixed models will be used in the analysis of the longitudinal QOL data. However, calculations based on the 2-sample t-test provide a conservative approximation for the power to detect treatment differences. Assuming at least 350 subjects per treatment group, GUIDE-IT will have >90% power for detecting a treatment difference of ¼ standard deviation. For many of the QOL instruments being proposed for this study, a treatment effect size equal to ¼ of a standard deviation is a reasonable benchmark for a clinically meaningful change.

Figure 5. Power curves for secondary endpoints

8.7 Statistical Analysis: General Approach

Statistical analysis will be performed by the GUIDE-IT data coordinating center (DCC) at Duke Clinical Research Institute (DCRI). All major treatment comparisons between the randomized groups in this trial will be performed according to the principle of "intention-to-treat;" that is, subjects will be analyzed (and endpoints attributed) according to the treatment strategy to which patients are randomized, regardless of subsequent additional post-randomization treatment and medical care. Statistical comparisons will be performed using 2-sided significance tests. Additional perspective regarding the interpretation of the data will be provided through extensive use of confidence intervals and graphical displays.

Baseline demographic and clinical variables will be summarized for each randomized arm of the study, for example: relevant descriptors from the history, physical and laboratory examination; CV risk factors; co-morbidity descriptors; and course of the patient's symptoms. Descriptive summaries of the distribution of continuous baseline variables will be presented in terms of percentiles (e.g., median, 25th and 75th percentiles), while discrete variables will be summarized in terms of frequencies and percentages. Because randomization is expected to produce excellent balance at baseline between the two arms of the trial, statistical comparisons of treatment groups with respect to baseline characteristics will be more informal. For comparisons of continuous baseline variables, emphasis will be given to nonparametric procedures such as the Wilcoxon rank sum test. Group comparisons with respect to discrete baseline variables will use the conventional chi-square test or Fisher's Exact Test as appropriate.

8.8 Analysis for the Primary Hypothesis

The statistical comparison of the two randomized arms with respect to the primary endpoint will be a time-to-event analysis, and therefore will be based on the time from randomization to the first occurrence of CV death or HF hospitalization. The Cox proportional hazards regression model will be the primary tool to analyze and assess outcome differences between the two treatment arms. A hazard ratio and 95% confidence interval for summarizing the difference in outcomes between the two treatment arms will be computed using the Cox model. This comparison will constitute the primary statistical assessment of the effect of biomarker guidance versus usual care on overall clinical outcomes. The Cox model will include an indicator variable for treatment group and baseline adjustment variables for age, sex, NT-proBNP, diabetes mellitus and ejection fraction.

In order to select the best set of adjustment covariates, we reviewed prognostic models from other large datasets in chronic HF. We selected covariates based upon the importance of choosing variables with

minimal missing data and adjusted the primary analysis for the following baseline variables: age, sex, NT-proBNP, ejection fraction, and diabetes mellitus.

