4.2 Inclusion Criteria

- Age \geq 18 years
- Most recent LVEF ≤ 40% by any method within 12 months of randomization
- High risk heart failure as defined by the following criteria
 - A Heart Failure Event in the prior 12 months, defined as any one of the following:
 - HF Hospitalization
 - Treatment in the Emergency Department (or equivalent) for Heart Failure
 - Outpatient treatment for heart failure with intravenous diuretics

AND

- NT-proBNP > 2000 pg/mL or BNP > 400 pg/mL at any time during the 30 days prior to randomization
- Willing to provide informed consent

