6.1 Screening

Clinical site staff will screen patients in both the inpatient and outpatient setting to identify high risk patients with systolic heart failure. If identified during a heart failure hospitalization, patients will not be randomized until the time of hospital discharge. A screening log will be maintained at each site. Eligible patients will provide written informed consent prior to randomization.

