6.3 Study Visits

6.3.1 Baseline

Baseline assessments will occur at the time of randomization and will include:

- Focused physical examination
- CV medication history
- Serum creatinine, blood urea nitrogen (BUN), and electrolytes (local laboratory)
- NT-proBNP (local laboratory)
- Health Related QOL questionnaire (as described in 6.7)
- 6 minute walk test
- Biomarker and DNA collection for biorepository (as described in 6.4)

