8.4 Anticipated Effect Size

We planned the sample size to detect a relative reduction in the 1-year event rate of 0.20. The power simulations shown below also examine the power with 15% relative reductions. Simulations with relative event rate reductions greater than 25% typically resulted in power greater than 99%. Results are based on 1,000 simulated data sets in each scenario with a 2-sided Type I error rate of 0.05 (Table 2). The estimated power is based on the proportion of simulations using the Cox regression model Wald chi-square p-value < 0.05. It is expected that the final subject enrollment will be followed for 12 months resulting in follow-up times varying from 12 to 24 months. However, to illustrate the power increase of additional follow-up, we have examined scenarios with 24 months follow-up on all patients.

Based on our best estimates for event rates and enrollment with a 20% reduction in events from a 1-year rate of 40% in the control group to 32% in the biomarker-guided group, we anticipate having 89.4% power with the proposed sample size of 1,100 subjects. With the same event and enrollment rates, we would have a slight increase in power to 91.2% if every subject was followed for 24 months. If per site enrollment is lower than we project at 1 patient per site per month and is closer to 0.75 patients per site per month, Table 1 shows that we can still achieve our target number of primary outcome events by extending the study duration by 10 months. Alternatively, we will have the option of adding more sites in order to maintain total study enrollment at 35 patients per month.

Although GUIDE-IT has been powered for the primary endpoint of time-to-CV death or HF hospitalization, a key secondary endpoint is the time to all-cause mortality. The power for this endpoint was evaluated with simulations as described above. With an assumed 1-year all-cause mortality rate of 25% in the control group, we estimated the power at 86.0% and 96.3% to detect relative event rate reductions of 25% and 30%, respectively, which are consistent with the treatment effect seen in a recent meta-analysis of biomarker-guided therapy.

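### The primary Cox model is valid, but it leaves out baseline creatinine, scheduled for every patient, and randomization at HF discharge versus outpatient; adding them is a cheap efficiency gain

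*Protocol*

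**What the plan says.** Section 8.8 does not leave the covariates open. It states: "The Cox model will include an indicator variable for treatment group and baseline adjustment variables for age, sex, NT-proBNP, diabetes mellitus and ejection fraction". The reasons given are a review of prognostic models in chronic HF and a preference for complete variables: "We selected covariates based upon the importance of choosing variables with" little missing data. Section 8.10 carries a similar Cox analysis over to the secondary time-to-event endpoints.

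The baseline visit in 6.3.1 includes "Serum creatinine, blood urea nitrogen (BUN), and electrolytes (local laboratory"), and Appendix A schedules these tests at both screening and Day 0 in both arms.

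Entry under 4.2 requires "A Heart Failure Event in the prior 12 months, defined as any one of the following": an HF hospitalization, emergency treatment, or outpatient intravenous diuretics. Section 6.1 screens inpatients and outpatients and adds: "If identified during a heart failure hospitalization, patients will not be randomized until the time of hospital discharge". Section 6.2 randomizes 1:1 by complete randomization and names no stratification factor.

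For power, 8.4 assumes a fall "from a 1-year rate of 40% in the control group to 32% in the biomarker-guided group" and concludes "we anticipate having 89.4% power with the proposed sample size of 1,100 subjects". The simulations described in 8.1, 8.3 and 8.4 mention no baseline covariate.

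**The concern.** Neither stated selection criterion explains why renal function is absent. It is measured in everyone at baseline, and the protocol does not say that the prognostic models it reviewed found renal function unimportant.

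The setting of randomization is a second visible source of differing risk. Sections 8.1 and 8.3 take the control rate from a trial that randomized patients at HF hospitalization, yet 4.2 and 6.1 also admit outpatients whose last HF event may be up to 12 months old. With no stratification, covariate adjustment is the only means in the design of using that information.

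What is at stake is efficiency. When a prognostic factor is left out of a Cox model, the treatment effect being estimated lies slightly closer to 1 and the test is somewhat less powerful than it could be. That matters most in the 15% reduction rows of Table 2, where stated power is only 57.7% to 77.2%.

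**Working it through.** **Inputs from the protocol.** 1,100 patients, 1:1; 1-year rates 40% and 32%; exponential event times; loss to follow-up and non-CV death 4% per year each; 5% switching arms uniformly over 2 years; 35 patients per month; follow-up 12 to 24 months; Cox Wald test at two-sided 0.05; 566 events; stated power 89.4%.

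**Inputs assumed.** The prognostic strength of the two omitted factors, and the share of patients randomized at discharge. The protocol gives neither.

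**Step 1: reproduce the stated power.**
- HR = ln(0.68)/ln(0.60) = 0.755.
- Closed form without switching: Φ(√566/2 × |ln 0.755| − 1.96) = Φ(11.90 × 0.281 − 1.96) = Φ(1.38) = 91.7%. This is high because it ignores drop-in and drop-out.
- Simulating the protocol's full design (2,500 runs) gives 89.2% and 566 events, against 89.4% and 566 stated. The 24-month version gives 90.6% and 604 events, against 91.2% and 605.
- With 1,000 runs, the stated figure has a Monte Carlo standard error of √(0.894 × 0.106/1000) ≈ 1 point.

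The stated figure therefore reproduces, with no covariates and no patient heterogeneity.

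**Step 2: add the two factors.** In the same simulation, renal function is a standard normal variable and setting is a 50/50 binary. Both are independent, so their strengths are read as what remains beyond the five covariates. A Cox model without them is compared with one including them (2,000 paired runs per row; standard error of the gain 0.2 to 0.7 points). The control rate is held at 40%.

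| Renal HR per SD | Setting HR | Gain, conditional HR fixed at 0.755 | Gain, marginal rates fixed at 40% vs 32% |
|---|---|---|---|
| 1.0 | 1.0 | −0.1 | 0.0 |
| 1.1 | 1.2 | 0.9 | 0.7 |
| 1.2 | 1.3 | 1.4 | 0.7 |
| 1.3 | 1.5 | 3.0 | 2.4 |
| 1.4 | 1.7 | 3.6 | 3.4 |
| 1.5 | 2.0 | 5.9 | 6.6 |

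**Step 3: put the existing covariates in as well.** Assume that the five covariates together carry a log-HR of 0.35 per SD and that half the patients are randomized at discharge.
- Conditional HR fixed: renal alone (log-HR 0.3 per SD) gains 2.0 points; setting alone gains 0.6 (HR 1.5) or 2.4 (HR 2.0); both gain 2.2 (1.5 and 0.2) to 4.9 (2.0 and 0.3). In the 40% vs 34% row the gains are 1.2 to 5.4 points.
- Marginal rates fixed at 40% vs 32% (1,500 runs): both factors gain 2.1 points (1.5 and 0.2) to 3.3 (2.0 and 0.3). If 85% are randomized at discharge, the gain is 1.1 to 1.3.
- Marginal rates fixed, with modest correlation between the new factors and the five covariates: about 0 to 2 points.

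**Step 4: chance imbalance in setting.** With half the patients randomized at discharge, the between-arm difference in that share has SD √(0.25 × 4/1100) = 3.0 points, so ±5.9 points at 95%. This shifts the log-HR by 0.059 × ln 1.5 = 0.02 to 0.059 × ln 2 = 0.04. The planned effect is |ln 0.755| = 0.28, with standard error 2/√566 = 0.084. The shift is at most about half a standard error, and the test's error rate already allows for it.

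**The case against.** The strongest reply is that nothing here is wrong. The list is pre-specified, it has a stated rationale, and type I error is unaffected. Nearly every trial collects prognostic variables that its model omits, and preferring complete variables is not a promise to include every complete variable. All of that stands, so this is a recommendation and not an error.

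Four stronger readings are tempting, and the protocol does not support them.

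- *Power is really below 89.4%.* With heterogeneity added and the conditional HR held at 0.755, the planned model can be made to show 83.5%. The treated 1-year rate is then 32.5%, so the effect tested is smaller than the one planned. With 40% and 32% held as marginal rates, the planned model gives 88.8% to 90.4% in the same scenarios.
- *The primary HR is biased.* Estimates of 0.766 to 0.778 without the extra factors, against 0.762 to 0.765 with them, reflect non-collapsibility: two slightly different quantities. The shift is at most about 0.015, and the 95% confidence limits lie at exp(±1.96 × 0.084), about −15% and +18% of the HR.
- *A definite number of points is being thrown away.* The gain depends wholly on assumed strengths, and the range includes zero. Section 8.2 expects patients to be identified around acute HF and randomized soon after discharge, which may leave little variation in setting. Section 4.2 also requires a raised natriuretic peptide within 30 days, and NT-proBNP is already in the model.
- *Type and date of the qualifying event are on file for everyone.* Sites must know them to establish eligibility, but 9.2 mentions only relevant history among the forms. A patient may also have had several qualifying events, so recency would need a further rule.

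The renal part survives these points. The setting part survives only if the variable is captured.

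**Conclusion.** The point holds as an efficiency improvement to a valid model. Baseline creatinine is scheduled for all patients, and neither stated criterion in 8.8 explains its omission. Discharge versus outpatient randomization is a reasonable second candidate on weaker ground.

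The expected gain is about 0 to 3 points of power for weak-to-moderate effects (up to a renal HR of 1.3 per SD and a setting HR of 1.5) and up to about 6 for strong ones. It is towards the lower end if the factors correlate with the existing covariates or most patients enter at discharge. A reader might infer that the stated power or the primary hazard ratio is compromised; neither is.

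**What to change.** Before any outcome comparison, amend 8.8 and the SAP as follows.

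1. Add log-transformed baseline creatinine as one fixed covariate in the primary Cox model. Name creatinine rather than leaving a choice between creatinine and BUN, and state how a missing value is handled; the screening result could stand in for a missing Day 0 result.
2. If the eCRF records it, add one binary covariate for randomization at HF-hospitalization discharge versus as an outpatient. Fix its form now, with no later choice between covariate and stratum based on the data.
3. Use the same set in the Cox models for the secondary time-to-event endpoints.

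If either factor was considered and rejected, a sentence saying why would also close the point. The change needs no extra patient or procedure. It costs one or two terms against about 566 events, a slightly longer covariate list and a few missing laboratory values.

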8.9 Supportive Analyses of the Primary Endpoint

If the data provide evidence of an overall difference in outcome between randomized arms, we will examine whether the effect is similar for all patients, or whether it varies according to specific patient characteristics. In particular, we will focus on whether the relative benefit differs according to patient age, sex, race, co-morbidity, and selected risk factors. These analyses will use the Cox model by testing for interactions between the randomized groups and specific baseline variables. In addition to the statistical hypothesis testing, Kaplan-Meier survival estimates will be constructed based on the time from randomization to the first occurrence of CV death or HF hospitalization.

8.10 Analysis of Secondary Endpoints

The analyses for the time-to-event secondary endpoints will be similar to those outlined for the primary endpoint using the time from randomization through the first occurrence of any component of a specific secondary endpoint (or censoring) as the response variable, and assessing group differences using the Cox proportional hazards model. The effect of the NT-proBNP-guided treatment strategy on these time-to-event secondary endpoints will be summarized using hazard ratios (with associated confidence intervals) computed from the Cox model. Kaplan-Meier curves will be constructed to display the cumulative event rates of the two treatment groups. For analysis of the total days alive and out of the hospital endpoint, we will apply the inverse probability weighted estimators of Bang and Tsiatis to account for the potential bias due to censored and incomplete data.⁵⁰

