7.2 Secondary Endpoints

- Time to All-cause mortality
- Recurrent hospitalizations
- Days alive and not-hospitalized for CV reasons
- Time to CV death
- Time to first HF hospitalization
- Health Related QOL
- Resource utilization, cost and cost effectiveness
- Safety

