8. STATISTICAL CONSIDERATIONS

8.1 Determination and Justification of Sample Size

Several design factors and research objectives have been considered in developing an appropriate sample size for the study. First, patient enrollment has been determined so there would be a sufficient number of endpoints to provide a high degree of confidence for testing the primary hypothesis. Second, the statistical power for secondary endpoints has been considered, including the EQOL endpoints. Finally, the sample size has been determined to provide a reasonable level of confidence for detecting clinically important differences in outcome between the two strategies—even if current projections of enrollment rates and hypothesized differences in clinical outcomes between the two arms prove to be optimistic.

Based on the anticipated patient population, we have projected a 1-year CV death and HF hospitalization rate of 40% for subjects randomized to the usual care arm. We estimate our patient population will be similar to that on the EVEREST study, a contemporary multicenter trial of patients with systolic HF randomized at the time of HF hospitalization and followed for a median of 10 months.⁴⁸ In EVEREST, the event rate for CV death or HF hospitalization at 10 months was 41%. Given that the meta-analysis of Felker et al. found an aggregate reduction of about 30% in all-cause mortality with biomarker-guided therapy, the impact of biomarker-guided therapy can conservatively be expected to reduce the primary composite endpoint (which we expect to be more sensitive to the effects of the biomarker-guided strategy than all-cause mortality) by 20% (from 40% to 32% at 1 year).

Based on the event rates for each arm discussed above, we have determined the sample size required to provide high power for detecting the postulated 20% relative risk reduction. As we recognize that the actual event rates and the outcome differences between the two testing strategies in GUIDE-IT may vary somewhat from these estimates, and we have determined the power of the study under several different combinations of enrollment rates, event rates and effect sizes. We have conducted the power analyses using simulation studies to mimic the key features of GUIDE-IT. As the primary treatment comparisons will be based on a time-to-event endpoint using the Cox proportional hazards model, we created 1,000 data

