8.3 Projected Event Rates

In EVEREST, the event rate for CV death or HF hospitalization at 10 months was 41%. Based on a similar patient population, we have assumed a 1-year event rate with a 40% control arm, which we believe is a conservative estimate. Unlike EVEREST, GUIDE-IT will require elevated natriuretic peptide levels during the

index hospitalization, a powerful marker of increased risk, suggesting GUIDE-IT will have a higher event rate than EVEREST. Power simulations were conducted varying this rate from 35% to 45%. Event times were created using randomly generated exponential variables. The non-CV death and the loss-to-follow-up rates were generated as independent exponential random variables with 1-year event rates of 4% for each variable. In the simulations, the primary outcome variable was censored if the non-CV death or loss-tofollow-up occurred first. The non-CV death rate was based on unpublished data from EVEREST. Drop-in and drop-out rates were assumed to be distributed uniformly in 5% of subjects over the 2-year follow-up. At the time of drop-in or drop-out, the hazard rate was switched to the rate for the other treatment group.

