8.11 Multiple Comparisons and Composite Endpoints

With the primary hypothesis and the various secondary endpoints, there is a multiplicity of analyses to be performed and an increased probability that at least one of the comparisons could be "significant" by chance. There are adjustments (e.g., based on the Bonferroni inequality) that can be used to preserve the overall type I error level by adjusting for the multiplicity of secondary endpoints by requiring small significance levels for every comparison. We will be conservative in the interpretation of these analyses, taking into account the degree of significance, and looking for consistency across endpoints. Also, we have pre-specified the primary and secondary outcome variables to help avoid over-interpretation and to reduce the problems inherent with multiple testing. A related issue is the interpretation of composite endpoints in clinical trials. To understand the importance of the components of the primary endpoint, we will estimate the treatment effect and frequency of each component (CV mortality and HF hospitalization) separately. Based on the prior biomarker-guided studies in HF, we have pre-specified age (\geq 75 or < 75 years of age) as a key subgroup of interest. The examination of this subgroup will include a formal test of interaction with the Cox regression model. Hazard ratio plots with point estimates and 95% confidence intervals will be used to examine the consistency of the treatment effect across subgroups.

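### Kaplan-Meier display of first HF hospitalization treats earlier death as censoring, so the displayed cumulative rate would be too high, by roughly 4 to 9 points in usual care at 2 years under the planning rates

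*Protocol*

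**What the plan says.** Section 7.2 of the protocol lists "Time to first HF hospitalization" and "Time to CV death" among the secondary endpoints, next to all-cause mortality. Section 8.10 analyses all time-to-event secondary endpoints alike. It takes "the first occurrence of any component of a specific secondary endpoint (or censoring) as the response variable", compares the arms by Cox hazard ratios, and then adds: "Kaplan-Meier curves will be constructed to display the cumulative event rates of the two treatment groups".

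Section 8.11 promises component results as well: "we will estimate the treatment effect and frequency of each component (CV mortality and HF hospitalization) separately".

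For the primary composite, section 8.9 says: "Kaplan-Meier survival estimates will be constructed based on the time from randomization to the first occurrence of CV death or HF hospitalization". That sentence speaks of survival estimates and does not call them cumulative event rates.

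No section mentions competing risks or cumulative incidence functions. The only explicit handling of a competing death is in the power simulations of section 8.3, where "the primary outcome variable was censored if the non-CV death" came first.

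**The concern.** In section 8.10 a patient's follow-up ends either in the event or in censoring. A patient who dies without an HF hospitalization is therefore censored at death. Kaplan-Meier treats censored patients as still able to have the event later. That is reasonable for loss to follow-up but not for death. One minus Kaplan-Meier then estimates the risk in a hypothetical population in which nobody dies before hospitalization. The section says the curve shows the cumulative event rate, which is the proportion of patients actually hospitalized by a given time. Method and stated quantity do not match.

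The mismatch matters in proportion to mortality, and section 8.4 assumes 25% all-cause mortality at 1 year in the control group. At stake is how readers understand the absolute HF hospitalization rates and the gap between the two curves. The hazard ratio and the test are not at stake.

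**Working it through.** **Inputs from the protocol**
- 1-year composite rate: 40% usual care, 32% guided (8.1).
- 1-year all-cause mortality: 25% in control, with a 25% relative reduction as one scenario, giving 18.75% guided (8.4).
- Non-CV death 4% and loss to follow-up 4% at 1 year, all times exponential (8.3).
- Follow-up 12 to 24 months (6.3.2); 1,100 patients.

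**Step 1: reproduce the plan's own figure.** A simulation as in 8.3 (exponential times, 5% cross-over uniform over 2 years, accrual of 35 per month, Cox Wald test, 2,000 runs) gave 89.9% power and 566 events. The protocol states 89.4% and 566. With 24 months for everyone it gave 90.8% and 606 events, against 91.2% and 605. The planning rates are therefore read as intended.

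**Step 2: yearly hazards, −ln(1 − p)**
- Composite: usual care −ln 0.60 = 0.511; guided −ln 0.68 = 0.386.
- Non-CV death: −ln 0.96 = 0.041.
- All-cause death: control −ln 0.75 = 0.288; guided −ln 0.8125 = 0.208.
- CV death: control 0.288 − 0.041 = 0.247; guided 0.208 − 0.041 = 0.167.

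**Step 3: the assumption.** The protocol does not say how many CV deaths come before a first HF hospitalization. Let c be that hazard. I vary c from 0.05 to 0.247 per year; the upper end is the control CV-death hazard if CV death is equally frequent before and after hospitalization.

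**Step 4: formulas.** Hospitalization hazard h = composite hazard − c. Competing death hazard d = c + 0.041.
- One minus Kaplan-Meier: 1 − exp(−h t).
- Cumulative incidence: h/(h + d) × [1 − exp(−(h + d) t)].

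Example, usual care, c = 0.20, t = 2: h = 0.311, d = 0.241, h + d = 0.552. One minus Kaplan-Meier is 1 − 0.537 = 46.3%. Cumulative incidence is 0.5634 × (1 − 0.3318) = 37.7%. The excess is 8.6 points.

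**Step 5: first HF hospitalization at 2 years** (one minus Kaplan-Meier / cumulative incidence / excess in points), same c in both arms

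| c per year | Usual care | Guided |
|---|---|---|
| 0.05 | 60.2 / 55.8 / 4.4 | 48.9 / 45.2 / 3.7 |
| 0.10 | 56.0 / 49.8 / 6.3 | 43.5 / 38.4 / 5.1 |
| 0.15 | 51.4 / 43.7 / 7.7 | 37.6 / 31.7 / 5.9 |
| 0.20 | 46.3 / 37.7 / 8.6 | 31.0 / 25.0 / 6.0 |
| 0.247 | 41.0 / 32.0 / 9.0 | 24.2 / 18.7 / 5.6 |

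If the guided arm's c is instead scaled by the composite hazard ratio 0.386/0.511 = 0.755, its excess runs from 3.3 (c = 0.05 × 0.755 = 0.038) to 6.1 points. At 1 year the excess is 1.5 to 2.9 points in usual care and 1.1 to 1.8 in the guided arm.

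**Step 6: the difference between arms.** With the mortality-implied hazards (c = 0.247 and 0.167), the 2-year difference by Kaplan-Meier is 41.02 − 35.45 = 5.57 points. By cumulative incidence it is 31.97 − 29.45 = 2.52 points. With the same c in both arms, the displayed difference is too wide by 4.39 − 3.73 = 0.7 points (c = 0.05) up to 9.04 − 5.56 = 3.5 points (c = 0.247).

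**Step 7: other endpoints at 2 years.** CV death: 39.0% against 37.5% in control (1.4 points, from unrounded values) and 28.4% against 27.3% in guided (1.1 points). Primary composite: 64.0% against 61.9% in usual care (2.1 points) and 53.8% against 51.9% in guided (1.9 points).

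**Sensitivity.** If CV death is 2 to 5 times as frequent after an HF hospitalization as before, with total mortality held at the planned level, the 2-year excess is 8.0 to 8.9 points in control and 5.2 to 5.9 in guided (both mortality scenarios). If the control composite rate is 35% or 45%, the limits that section 8.3 considers, the control excess is about 7 to 11 points at 25% mortality.

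**The case against.** The strongest reply is that the curve is only a display. Section 8.10 summarizes the effect by Cox hazard ratios, and censoring at competing death is a legitimate way to estimate a cause-specific hazard ratio. The component frequencies in 8.11 are not tied to a curve and could be simple counts. The economic model in 8.13 does not use the HF hospitalization curve. HF hospitalization is also reported beside all-cause mortality, CV death, days alive and not hospitalized, and the exploratory global rank and win ratio, so no conclusion rests on it alone. All of this stands and limits the weight of the point. It does not make the curve show what section 8.10 says it shows. Nor is this a detail left to a later plan, since the protocol itself names both the method and the quantity.

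Four stronger readings are tempting, but the document does not support them.
- A reader might quote one firm figure, such as 6 to 9 points. The size depends on how many deaths precede hospitalization, which the protocol does not give. At c = 0.05 the usual-care excess is 4.4 points, and in the guided arm it is lower.
- A reader might blame the unequal excess on unequal mortality. With the same c of 0.20 in both arms it is still 8.6 against 6.0; lowering the guided arm's c to 0.151 only moves 6.0 to 5.9. In this set-up the different composite hazards do most of the work.
- A reader might say that planned risk differences or numbers needed to treat will be wrong. The protocol plans neither.
- A reader might extend the criticism in full to CV death and the primary composite. Their gaps are small, and section 8.9 promises only survival estimates. The censoring in 8.3 describes the simulations, not the analysis.

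**Conclusion.** The point holds for the display of first HF hospitalization in section 8.10. Followed as written, the curve would overstate the cumulative rate. The direction is certain whenever some patients die before hospitalization; the size is conditional. It rests on the planning rates, constant hazards, and an assumed hazard of CV death before hospitalization of 0.05 to 0.25 per year. On that basis the 2-year excess is roughly 4 to 9 points in usual care and 3 to 6 in the guided arm. In every scenario of Steps 5 and 6 the excess is larger in usual care, so the displayed gap between the arms would look wider than the true one.

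For CV death and the primary composite the effect is real but minor. The hazard ratios, the primary test and the sample size are unaffected. This is worth correcting, but it does not threaten the trial's main conclusion.

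**What to change.** In section 8.10, state that first HF hospitalization will be displayed by Aalen-Johansen cumulative incidence curves by arm, with death from any cause as the competing event. Apply the same to any HF hospitalization frequency under section 8.11 that is read from a curve. CV death may be shown the same way with non-CV death competing, although little will change. Keep Kaplan-Meier for all-cause mortality, which has no competing event, and keep the Cox hazard ratios and the primary analysis as they are.

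The cost is a sentence or two of text and a standard procedure. Deaths and hospitalizations are already collected and go to blinded adjudication (sections 6.5 and 7.4.2), so no new data are needed.
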